15.6.5 Planned Interim Analysis

An interim analysis for futility will be performed based on the Simon's 2-stage optimal design when 9 efficacy evaluable patients are evaluable for ORR. The study will stop early if 2 or fewer responders are observed. If 3 or more responders are confirmed before the planned interim analysis and the safety profiles of both drugs are acceptable, the study will continue to Stage 2 and a normal interim analysis may be waived. There will be no enrollment gap for the interim analysis.

At the final analysis with 34 efficacy evaluable patients, the study will claim preliminary efficacy to warrant further study if 9 or more responders are observed.

	Threshold
Interim Analysis	Continue to enroll if ≥ 2 responders among the first 9 efficacy evaluable patients
Final Analysis	Reject H_0 if ≥ 9 responders among n=34 patients

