2.6 Study Design

2.6.1 Overall Design

This is a single-arm, multicenter, phase 2 study of lenvatinib in combination with pembrolizumab (lenvatinib 20 mg/day + pembrolizumab 200mg q3weeks) in subjects with unresectable advanced or metastatic nccRCC who have not received any chemotherapy for advanced disease.

A Simon's Two-Stage Design will be implemented in approximately 34 enrolled subjects. Nine subjects will be enrolled in Stage 1. If there are at least 2 responders

as assessed by ORR, the study will proceed to Stage 2 in which 25 more subjects may be enrolled. Otherwise, the study will stop early for futility. In the final analysis of 34 subjects, at least 9 responders are required to show a statistically significant improvement of ORR over historical control in the same patient population (one-sided type I error of 5% and targeting for 80% power).

This study consists of 3 phases:

1. Pre-treatment phase (Screening Periods)
2. Treatment phase (starting Cycle 1 Day 1)
3. Post-treatment phase (End of Treatment Visit and survival follow-up)

The pre-treatment phase is planned to last no longer than 21 days and will include a screening period to establish protocol eligibility.

The treatment phase will begin at the time of study drug administration on Day 1 of Cycle 1 and continue in 21-day (3-week) cycles until completion of the off-treatment assessments (within 30 days after the last study drug administration). Lenvatinib 20 mg/day will be administered orally on a daily basis and pembrolizumab 200 mg will be infused once every 3 weeks. Subjects will undergo safety and efficacy assessments. Toxicity will be managed by treatment interruption, dose reduction and/or treatment discontinuation. Subjects who discontinue one of the study drugs due to its toxicities may continue to receive the other study drug as long as they demonstrate clinical benefit. Subjects will discontinue both study drugs at the time of confirmed disease progression, development of unacceptable toxicity, withdrawal of consent, or study termination. Subjects may be treated with pembrolizumab for a maximum of 35 cycles or approximately 2 years, but treatment with lenvatinib can continue beyond 2 years if the subject does not meet other treatment discontinuation criteria.

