15.3 Statistical Hypotheses

In this population, ORR in first line treatment in locally advanced or metastatic non-clear cell RCC (nccRCC) is assumed to be 15%. Most published ORR prior to 2019 was at ~8%. However, the most recently reported data in Feb, 2019, on Keynote 427 cohort B nccRCC, a phase II study, was 24.8% Hence, the ORR in this study is estimated $\geq 35\%$, which is deemed a clinical meaningful improvement. Hence, the null and alternative hypotheses are set as follows:

$$H_0: \text{ORR} \leq 15\% \text{ versus } H_a: \text{ORR} \geq 35\%$$

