15.4 Sample Size Determination

The Simon's Two-Stage optimal design was adopted to design the study with a one-sided type I error rate of 5% and targeting for 80% power. Approximately 34 efficacy evaluable subjects will be enrolled. During the 1st stage, 9 subjects will be enrolled and if there are ≥ 2 responders as assessed by ORR, the study will proceed to Stage 2 in which 25 new subjects will be enrolled; otherwise, the study will stop early for futility. In the final analysis of 34 efficacy evaluable subjects, ≥ 9 responders are required to claim preliminary efficacy of the treatment combination over historical control in the same patient population.

The actual alpha level was 0.047 and the actual power was 0.811. The early termination probability is estimated at 0.5995 if null is true and the average sample size is around 19.

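### Section 15.6.5 stops the trial at 2 or fewer responders of 9, but the design and that section's own table continue at 2 or more; following the text cuts power from 0.811 to 0.632

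*Combined protocol and SAP*

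**What the plan says.** The design is a Simon optimal two-stage design with one-sided alpha of 5% and 80% target power, testing an ORR of at most 15% against at least 35% (Sections 15.3 and 15.4). Stage 1 has 9 patients, Stage 2 adds 25, and the final analysis rejects the null with 9 or more responders among 34.

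The interim rule appears in four places:

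- Section 2.6.1, Overall Design: "If there are at least 2 responders", the study goes on to Stage 2; otherwise it stops for futility.
- Section 15.4, Sample Size Determination: "if there are ≥ 2 responders as assessed by ORR, the study will proceed to Stage 2"; otherwise it stops.
- Section 15.6.5, threshold table: "Continue to enroll if ≥ 2 responders among the first 9 efficacy evaluable patients".
- Section 15.6.5, prose: "The study will stop early if 2 or fewer responders are observed". The next sentence lets the study continue, with the formal look possibly waived, once 3 or more responders are confirmed ahead of the interim and safety is acceptable.

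Section 15.4 also gives the operating characteristics: "The actual alpha level was 0.047 and the actual power was 0.811", with an early termination probability of 0.5995 under the null and an average sample size of about 19.

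**The concern.** Three statements of the rule continue with 2 responders among 9, and one stops. The one that stops is the running text of the section devoted to the interim analysis, which is where the person conducting that analysis would look first. The sentence after it uses a bar of 3, which fits stopping at 2, so a reader of the prose alone would see nothing amiss.

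This is the only formal efficacy decision before the final analysis. If 2 of 9 is observed, either action can be defended from the document and either can be criticised as chosen after seeing the data. If the prose is followed, the trial no longer has the power it claims, and an active regimen is more likely to be dropped in a population for which Section 2.2 says there is no first-line standard of care.

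**Working it through.** **Inputs.** Null ORR p0 = 0.15 and alternative p1 = 0.35 (Section 15.3); n1 = 9, n2 = 25, N = 34, reject with 9 or more responders (Section 15.4). The minimum number of Stage 1 responders needed to continue is c: c = 2 under Sections 2.6.1 and 15.4 and the 15.6.5 table, c = 3 under the 15.6.5 prose.

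**Formulas.** With X1 ~ Bin(9, p) and X2 ~ Bin(25, p) independent:

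- P(reject) = Σ over x from c to 9 of P(X1 = x) × P(X2 ≥ 9 − x)
- P(early stop) = P(X1 ≤ c − 1)
- Expected N = 9 + 25 × [1 − P(early stop)]

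**Step 1: reproduce the stated figures with c = 2.**

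- Early stop at p0: 0.85⁹ + 9 × 0.15 × 0.85⁸ = 0.2316 + 0.3679 = 0.5995 (stated 0.5995).
- Expected N at p0: 9 + 25 × (1 − 0.5995) = 19.0 (stated about 19).
- Alpha: 0.0474 (stated 0.047).
- Power: 0.8107 (stated 0.811).

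All four agree. A search over two-stage designs with total N up to 41 also returned this design (9 patients, continue at 2 or more, 34 in total, reject at 9 or more) as the Simon optimum for these error rates.

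**Step 2: change only the interim rule to c = 3.** This removes the paths that pass through exactly 2 of 9.

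- At p1: P(X1 = 2) = 36 × 0.35² × 0.65⁷ = 0.2162, and P(X2 ≥ 7) = 0.8266. The power lost is 0.2162 × 0.8266 = 0.1787, so power = 0.8107 − 0.1787 = 0.6320.
- At p0: P(X1 = 2) = 36 × 0.15² × 0.85⁷ = 0.2597, and P(X2 ≥ 7) = 0.0695. The alpha removed is 0.2597 × 0.0695 = 0.0181, so alpha = 0.0474 − 0.0181 = 0.0294 from unrounded values.
- Early stop at p0: 0.5995 + 0.2597 = 0.8591 from unrounded values. Expected N = 9 + 25 × (1 − 0.8591) = 12.5.
- Early stop at p1: 0.1211 + 0.2162 = 0.3373.

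| Quantity | Stop at ≤1 (design, table) | Stop at ≤2 (15.6.5 prose) | Stated in 15.4 |
|---|---|---|---|
| Alpha | 0.0474 | 0.0294 | 0.047 |
| Power at 35% | 0.8107 | 0.6320 | 0.811 |
| Early stop at 15% | 0.5995 | 0.8591 | 0.5995 |
| Expected N at 15% | 19.0 | 12.5 | about 19 |
| Early stop at 35% | 0.121 | 0.337 | not stated |

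None of the stated characteristics is matched by the prose rule.

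**The case against.** The intended rule is easy to recover: three of the four statements agree, all four stated operating characteristics support them, and 15.6.5 says it follows the Simon design. The design and its arithmetic are sound. That is true, and it settles which wording is the outlier. It does not remove a plain instruction to stop from the section that governs the interim.

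The sentence about 3 or more responders can be read as a separate condition for skipping the formal look, which could sensibly be stricter than the bar for continuing. Taken alone that reading is possible, so the sentence does not prove a repeated error. But it follows directly on a rule that stops at 2 or fewer, and the two pair naturally as complements.

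The size also needs its baseline. The correct design already stops with probability 0.121 when the ORR is 35%, so the excess attributable to the prose is 0.216, about one trial in five, out of the total 0.337. Type I error is not inflated; it falls. Finally, the expected sample sizes assume accrual ends at 9 when the trial stops, while 15.6.5 provides for no enrolment pause, so actual numbers could be higher under either rule. Power and alpha are unaffected provided the decision uses the first 9 evaluable patients.

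**Conclusion.** The contradiction is real and concerns the go/no-go rule for the primary endpoint, so it must be corrected. The prose of 15.6.5 is the statement that is wrong, because only stopping at 1 or fewer yields the figures in Section 15.4. If the prose were followed, power would be 0.632 rather than 0.811, a loss of 17.9 percentage points that leaves it well below the 80% target, and about one trial in three would stop for futility at a true ORR of 35%, against about one in eight under the design. These figures assume that the stopping rule is binding, as its wording implies, that the final cut-off stays at 9 of 34, and that the true ORR is 35%. The disputed outcome, exactly 2 of 9, has a probability of roughly one in five to one in four under the two hypotheses.

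**What to change.** In the prose of Section 15.6.5, make the study stop if 1 or fewer responders are seen among the first 9 efficacy evaluable patients, and lower the waiver condition in the next sentence from 3 to 2 responders. The second change is sound because 2 confirmed responders already clear the futility bar. If the sponsor does want a stricter bar for skipping the formal look, the text should say so and state that 2 of 9 at the look still means continuing. The section will then agree with its own table, Sections 15.4 and 2.6.1, and the stated operating characteristics.

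The cost is two small wording changes and the IRB approval that the Statement of Compliance requires for any amendment. Sample size, procedures and the final analysis do not change. The correction should be in place before the Stage 1 responses are known.

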1.0 SCHEDULE OF ACTIVITIES

Screening tests may take place no more than 21 days prior to the first day of study treatment. Window for study visits during treatment is +/- 7 days.

	Screening	C1D1	D1 of each subsequent cycle	Q9 wks	EOT	FU ⁴
Informed consent	X					
H&P, PS	X					
Vital signs	X		X			
CBC	X	X	X		X	
Blood chemistry ⁹	X		X			
Pregnancy test ¹	X ³					
TSH	X		X			
INR	X		X			
Urinalysis	X					
UPCR		X	X			
ECG	X					
CT or MRI ⁸	X			X	X	
Pembrolizumab		X	X			
Lenvatinib ²		X-----X ²				
Research tissue collection ⁷	X					
Research blood collection	X ⁵	X ⁵	X ⁶		X	
Adverse events	X-----X					
Progression and survival						X

1. Women of childbearing potential only
2. Lenvatinib is to be self-administered daily on each day of every 21-day cycle
3. Within 72 hours prior to first dose
4. After coming off treatment, patients will be followed every 12 weeks +/- 1 week until death for survival. If patients discontinue treatment prior to progression, patients will continue to be followed by scans approximately every 9 weeks until progression or the start of another anti-cancer therapy.
5. To be drawn at screening or C1D1 (up to 14 days prior to the start of treatment)
6. C4D1 only
7. Archival from within 3 months (preferred), up to 6 months acceptable; if no biopsy has been performed in the 6 months prior to treatment start then an SOC biopsy should take place after a patient has been determined to be eligible for the trial, if safe and feasible. See section 10.0 for more details.
8. Scans should continue every 9 weeks regardless of cycle length. See Section 12 for further instructions of timelines for obtaining confirmatory scans. For responses, or progression, a confirmatory scan should be performed at least 4 weeks after the initial scan showing progression or response.
9. Albumin, alkaline phosphatase, total bilirubin (and direct bilirubin if total bilirubin is above ULN), bicarbonate, BUN, calcium, chloride, creatinine, glucose, phosphorus, potassium, total protein, AST, ALT, sodium

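### The average sample size of about 19 under the null assumes that accrual halts at nine evaluable patients, but the plan does not pause or cap accrual for the interim

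*Combined protocol and SAP*

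**What the plan says.** Section 15.4 adopts a Simon optimal two-stage design with a "one-sided type I error rate of 5% and targeting for 80% power". It reports an attained alpha of 0.047, power of 0.811 and an early termination probability of 0.5995 under the null, and adds that "the average sample size is around 19".

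Section 2.6.1 describes the stages in sequence. "Nine subjects will be enrolled in Stage 1", and 25 more may follow "If there are at least 2 responders"; otherwise the trial stops for futility. Section 15.4 says the same.

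Section 15.6.5 places the interim at nine efficacy-evaluable patients and states: "There will be no enrollment gap for the interim analysis". It gives no accrual cap and no rule for reporting patients who have entered beyond the ninth if the trial stops. Its table bases the decision on the first nine efficacy-evaluable patients and continues at two or more responders, but its text stops the trial at two or fewer.

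On timing, the Schedule of Activities (Section 1.0) sets scans every 9 weeks. Its footnote 8 adds that "a confirmatory scan should be performed at least 4 weeks after the initial scan showing progression or response".

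**The concern.** An expected size of 19 requires that nobody enters between the ninth evaluable patient and the futility decision. The stage 1 result cannot be known when the ninth patient starts treatment, because the first on-treatment scan is about 9 weeks later and a response seen then calls for another scan at least 4 weeks after that. If accrual carries on meanwhile, every futility stop happens with more than nine patients treated.

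The optimal design is the one that minimises expected enrolment under the null. A reader who takes 19 as the expected exposure to an inactive regimen would be given a figure that is somewhat too favourable for the trial as it will be run.

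**Working it through.** **Inputs from the documents.** Null and alternative response rates 0.15 and 0.35 (Section 15.3). Stage 1: 9 patients, continue at 2 or more responders. Total: 34, success at 9 or more (Sections 2.6.1 and 15.4, and the table in 15.6.5). Scans every 9 weeks, confirmation at least 4 weeks later (Section 1.0). Accrual not paused (Section 15.6.5).

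**Step 1: reproduce the plan's figures.** The early termination probability (PET) under the null is

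PET = P(X ≤ 1 | n = 9, p = 0.15) = 0.85⁹ + 9 × 0.15 × 0.85⁸ = 0.2316 + 0.3679 = 0.5995.

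The expected size is 9 + (1 − 0.5995) × 25 = 9 + 0.4005 × 25 = 19.01. Exact binomial calculation gives alpha 0.0474 and power 0.8107. A search over two-stage designs returns this same design (stop at 1 or fewer of 9; fail at 8 or fewer of 34) as the optimal one. All the figures in Section 15.4 reproduce.

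**Step 2: see what the 19 counts.** Written by branch, it is 0.5995 × 9 + 0.4005 × 34. The stopping branch carries exactly 9 patients.

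**Step 3: let accrual continue.** Let m patients enter while stage 1 is pending. A stop then occurs at 9 + m. A trial that continues still ends at 34. Hence

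E[N | null] = 0.5995 × (9 + m) + 0.4005 × 34 = 19.01 + 0.5995m.

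Each extra patient adds 0.60. If all of stage 2 entered before the decision (m = 25), the result would be 34.

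**Step 4: a range for m.** No accrual rate is stated, so one is assumed: 34 patients over 36, 24 or 12 months. The lag runs from the ninth patient's start of treatment: 9 weeks (first scan) or 13 weeks (first scan plus the minimum 4 weeks to confirm). With 4.345 weeks per month, m = rate × lag / 4.345.

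| Accrual assumed | Rate per month | Lag (weeks) | m | Treated at a stop (9 + m) | E[N] under the null |
|---|---|---|---|---|---|
| 36 months | 0.94 | 9 | 2.0 | 11.0 | 20.2 |
| 36 months | 0.94 | 13 | 2.8 | 11.8 | 20.7 |
| 24 months | 1.42 | 9 | 2.9 | 11.9 | 20.8 |
| 24 months | 1.42 | 13 | 4.2 | 13.2 | 21.6 |
| 12 months | 2.83 | 9 | 5.9 | 14.9 | 22.5 |
| 12 months | 2.83 | 13 | 8.5 | 17.5 | 24.1 |

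**Step 5: what does not move.** PET, alpha and power depend only on responses among the first 9 and among the 34. They keep their stated values if the decision uses the first 9 evaluable patients and a stop is honoured.

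**Step 6: the other rule in Section 15.6.5.** If the trial stopped at 2 or fewer responders, PET would be 0.859, alpha 0.029, power 0.632 and the expected size 12.5 + 0.86m, or about 14.2 to 19.8 over the same range of m. The stated 19 therefore belongs only to the two-or-more rule.

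**The case against.** The strongest reply is that nothing has been miscalculated. The 19 is the usual descriptor of this Simon design, every companion figure reproduces, and no threshold or analysis uses it. All of that stands, and it is why the point is minor.

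A second reply is that the no-gap sentence comes straight after the clause that lets the interim be waived once three or more responders are confirmed early. It might therefore cover only that case, while Sections 2.6.1 and 15.4 describe sequential enrolment. That reading is possible, but the sentence speaks of the interim analysis without restriction. The waiver also applies only when the trial continues, whereas extra patients raise the expected size only when it stops. If the narrow meaning was intended, the plan should say so.

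Third, the size is uncertain. Section 15.6.5 does not define when the decision is taken. A ninth patient without a response at the first scan has nothing to confirm, so 13 weeks will not always apply. The synopsis gives a study duration of 36 months but no accrual period. At the slow end, 20.2 hardly differs from about 19. This too stands, and limits the claim to a conditional range.

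Fourth, the 20 to 24 range presumes the two-or-more rule, which the text of Section 15.6.5 contradicts. This stands, and it means that the rule must be settled before any expected size is restated.

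**Conclusion.** The stated average size is right for a design that halts at nine and does not describe a trial that keeps enrolling. Under the two-or-more continue rule the expected size under the null is 19.0 + 0.60m. With the assumed accrual of 34 patients over 12 to 36 months and a lag of 9 to 13 weeks, that is about 20 to 24, with a futility stop at about 11 to 17 patients instead of nine. The formula follows from the documents; the range rests on the assumed rate and lag. These are counts of evaluable patients, so the replacements allowed in Section 15.5 would add to them.

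A reader might infer that Section 15.4 contains an arithmetic error, or that continuing accrual weakens the error rates. The documents support neither. The figures reproduce exactly, and the table in Section 15.6.5 already ties the decision to the first nine efficacy-evaluable patients. Alpha of 0.047, power of 0.811 and early termination probability of 0.5995 hold as long as the stop is binding, and the plan nowhere says that it is not.

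**What to change.** In order:

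1. Reconcile the sentence in Section 15.6.5 that stops at two or fewer responders with the two-or-more continue rule in its own table and in Sections 2.6.1 and 15.4. The expected size cannot be stated until this is done.
2. In Section 15.4, either label 19 as assuming an accrual pause at the ninth evaluable patient, or restate the expected size using the planned accrual rate and the time from the ninth patient's start to the decision. If accrual is in fact to be paused or capped, say so in Section 15.6.5 instead.
3. State how patients enrolled beyond the ninth will be reported if the trial stops. That they do not count towards the stage 1 decision is already in the table and needs only to be kept.

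Continuous accrual can remain. The cost is a few sentences of wording and, if the figure is restated, a slightly less favourable number. Sample size and final threshold do not change.

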15.6.6 Planned subset Analyses

Exploratory subset analysis on efficacy endpoints may be performed, for example, by race, by sex, by histological subtype.

15.6.7 Exploratory endpoint Analyses

A 2-sided 95% Clopper–Pearson CI will be constructed for CBR and DCR. DOR will be analyzed using the KM method described above.

15.7 Continuous monitoring for toxicity using a Pocock-type boundary

We will monitor the occurrence of intolerable toxicities (as defined below) in the 34 efficacy evaluable patients using a Pocock-type boundary for repeated testing for toxicity (20). This boundary is equivalent to testing the null hypothesis, after each patient, that the event rate is equal to 0.25, using a one-sided alpha level 0.016 test. The accrual will be halted if excessive numbers of intolerable toxicities are seen, that is, if the number of intolerable toxicities is equal to or exceeds boundary (b_n) out of a total of n patients treated and with full follow-up (see table below). This is a Pocock-type stopping boundary that yields the probability of crossing the boundary ≤ 0.05 when the rate of intolerable toxicities is equal to the acceptable rate of 0.25.

Number of Patients, n	1	2	3	4	5	6	7	8	9	10	11	12	13	14	15	16	17	18	19	20
Boundary, b_n	-	-	-	4	5	5	5	6	6	7	7	7	8	8	9	9	9	10	10	10
Number of Patients, n	21	22	23	24	25	26	27	28	29	30	31	32	33	34						
Boundary, b_n	11	11	11	12	12	13	13	14	14	14	15	15	15							

Intolerable toxicities include severe treatment-emergent adverse events which can't be resolved within 7 days, including

- Death
- Life-threatening adverse drug experience
- Inpatient hospitalization or prolongation of existing hospitalization
- A persistent or significant disability/incapacity (i.e., a substantial disruption of a person's ability to conduct normal life functions)
- Any other experience which, based upon appropriate medical judgment, may jeopardize the subject and may require medical or surgical intervention to prevent one of the outcomes listed above

